## 1) STUDY AIM, BACKGROUND, AND DESIGN ABSTRACT

This study aims to determine if application of Gebauer's Pain Ease or Gebauer's Ethyl Chloride numbing sprays will contaminate skin which has been prepped with chloraprep. Due to the recent national shortage of lidocaine we hope to be able to find a suitable alternative to lidocaine for topical analgesia during invasive procedures such as arterial lines and epidurals. Depending on the results of this study we will decide if it is safe to proceed to additional studies to determine if numbing sprays are effective alternatives to lidocaine for topical analgesia. Our plan is to compare the number of colony forming units (CFU) of bacteria that grow on a section of skin on the wrist and lower back prior to treatment, following chloraprep treatment, and following application of pain ease spray or ethyl chloride. Our hypothesis is that the sprays will not affect the sterility of the area and that there will not be a significant increase in bacterial growth after ethyl chloride or pain ease spray have been added to skin treated with chloraprep.

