#### 3) STUDY PROCEDURES

Our study will involve swabbing and culturing the skin of volunteers on the wrist where an arterial line is place, as well as on the lower back where an epidural is placed. First, a swab of the untreated area of wrist or lower back will be performed. Second, the section of skin will be treated with chloraprep according to standard procedure prior arterial line or epidural placement, and this treated skin will be swabbed. Third, the chloraprep-treated section of skin will be treated with numbing spray (either Gebaur's Ethyl Chloride or Pain Ease). For the Pain Ease group, the spray will be applied up to 10 seconds or until white appears (whichever comes first). If frosting appears, stop. The area that has been subsequently treated with chloraprep and numbing spray will then be swabbed. These swabs will be cultured by the HFHS microbiology lab on agar plates for 48 hours and the number of colony forming units (CFU) will be counted. The amount of bacterial growth will be compared between the untreated samples, chloraprep samples and the associated post-spray samples. Funding for the project will be from Gebauer, the manufacturer of the numbing sprays. Based on power analysis, for each spray, a sample size of 72 subjects with 6 swabs taken per subject (subsequent untreated, chloraprep, and numbing spray samples taken from the wrist and lower back from each subject) achieves 80 % power to detect an odds ratio of 24 using a two-sided McNemar test with a significance level of 0.05. The odds ratio is equivalent to a difference between two paired proportions of 0.115 which occurs when the proportion in cell 1,2 is 0.12 and the proportion in cell 2,1 is 0.005. The proportion of discordant pairs is 0.125. As there are two separate sprays being investigated independently, the final number of subjects will be 144, with 6 swabs taken per subject.

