## **Data Analysis and Statistical Considerations**

We will collect data on an excel spreadsheet. We will not collect any personal health information or identifying information for the participants.

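### The plan seeks a no-harm conclusion about sterility but names only a test of difference, with no margin or interval criterion, so a non-significant result rules out no stated rise in contamination

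*Combined protocol and SAP*

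**What the plan says.** Section 1 (study aim, background and design abstract) states the hypothesis as an absence of harm: "Our hypothesis is that the sprays will not affect the sterility of the area", and "there will not be a significant increase in bacterial growth after ethyl chloride or pain ease spray have been added". It then ties a decision to the outcome: "Depending on the results of this study we will decide if it is safe to proceed to additional studies".

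Section 3 (study procedures) gives the sample size. For each spray, 72 subjects "achieves 80 % power to detect an odds ratio of 24 using a two-sided McNemar test with a significance level of 0.05". The alternative is a paired difference of 0.115, made up of 0.12 in cell 1,2 and 0.005 in cell 2,1; "The proportion of discordant pairs is 0.125". On analysis, the section says only this: "The amount of bacterial growth will be compared between the untreated samples, chloraprep samples and the associated post-spray samples".

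The section headed data analysis and statistical considerations begins "We will collect data on an excel spreadsheet" and goes on to privacy. It names no test, margin, interval or decision rule.

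**The concern.** A McNemar test can show that contamination changed. Failing to reject does not show that it stayed the same. Because the hypothesis is worded as no significant increase, the natural reading is that p > 0.05 will count as support. The plan does not say so in words. If that reading is wrong, the plan has no decision rule at all, and the same correction is needed.

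The error that matters is to conclude that skin remains sterile when it does not, because the result opens the way to studies of the sprays for procedures such as arterial lines and epidurals. On the inferred reading, few subjects, lost plates and noisy cultures all make the favourable conclusion more likely. The plan limits the error only indirectly, through 80% power at an 11.5-point rise. Smaller rises are missed more often, and nothing says which rises would be acceptable.

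**Working it through.** **Inputs from section 3.** p12 = 0.12, p21 = 0.005, so discordance pd = 0.125 and difference d = 0.115; two-sided alpha 0.05; 72 subjects per spray.

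**Assumptions.** Cell 1,2 means no growth after chloraprep and growth after spray (the plan does not define it). Each subject gives one pair. Reverse discordance stays at 0.005 unless stated. The plan names no version of McNemar's test, so ranges run from the uncorrected to the exact test.

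**1. The plan's own figure.** n = [1.960·√pd + 0.842·√(pd − d²)]² / d² = (0.6930 + 0.2814)² / 0.115² = 71.8, so 72. By the same formula, power is 0.801 at 72 pairs and 0.980 at 144. The arithmetic is sound, and the stated 80% corresponds to one pair per subject.

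**2. Chance of no significant increase.** Exact enumeration over the discordant counts, with p12 = rise + 0.005:

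| True rise | 72 pairs, uncorrected | 72 pairs, exact | 144 pairs, uncorrected | 144 pairs, exact |
|---|---|---|---|---|
| 5 points | 58% | 84% | 24% | 38% |
| 7 points | 37% | 64% | 8% | 14% |
| 10 points | 16% | 32% | 1% | 2% |
| 11.5 points | 10% | 21% | 0.3% | 0.7% |

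With 72 pairs the chance passes 50% for rises below about 5.7 points (uncorrected) or 8.2 points (exact). The 144-pair columns treat wrist and back as independent, which is optimistic.

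**3. A result that does not depend on the version of the test.** Of 72 pairs, 6 become contaminated and 1 reverses.

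- Uncorrected: (6 − 1)/√7 = 1.89, p = 0.059.
- Exact: 2 × (1 + 7)/2⁷ = 0.125.
- Mid-p: 0.125 − 7/128 = 0.070.
- Net rise: 5/72 = 6.9%; Tango score 95% interval -0.3% to 15.9%.

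The result is non-significant on every version, yet the 11.5-point design rise is not excluded.

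**4. What an interval rule would do.** Chance that the Tango 95% upper limit lies below the margin, 72 pairs, no true effect, equal discordance each way (only the 6.25% case matches the plan's total of 12.5%; the others are assumptions):

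| Discordance each way | Margin 0.115 | Margin 0.05 |
|---|---|---|
| 1% | 98% | 26% |
| 2% | 93% | 26% |
| 3% | 88% | 24% |
| 6.25% | 71% | 20% |

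At margin 0.05, even no discordant pairs at all would fail (upper limit 0.0507). The passes in that column therefore come only from samples in which growth happens to fall after spraying.

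At margin 0.115 with reverse discordance 0.005, a true 5-point rise would pass 31% of the time, 7 points 13%, 10 points 3% and 11.5 points 1%.

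**The case against.** Four points can be made for the plan.

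- **The faulty rule is inferred.** The aim can be read as a question of detection, and the decision to proceed is left to judgement. This is true. But the hypothesis is framed as the absence of a significant increase, and no other criterion is given.
- **The 0.115 works as an implicit margin.** The stated n matches the uncorrected formula, and reversals should be rare (72 × 0.005 = 0.36 expected). With none, 4 against 0 is already significant (p = 0.0455). The worst non-significant result is then 3 against 0, with an upper limit of 0.1155, close to the design difference. This narrows the gap but does not close it, since even that limit does not exclude 0.115. One reversal, or the exact test (5 against 0: p = 0.0625, upper limit 0.152), takes it well above. The plan presents 0.115 only as a detectable difference.
- **The remedy fixes on any growth, although the plan also speaks of colony counts.** This is fair as a caution: counts could rise on plates that were already positive. The binary endpoint is, however, the one that the McNemar calculation implies.
- **The study only opens the way to further studies, in volunteers.** That limits the immediate stakes. But the go or no-go decision is the study's stated purpose.

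**Conclusion.** The concern holds. The test that the plan names cannot support the conclusion that it seeks, and no margin, interval criterion or decision rule fills the gap. The sample-size arithmetic is correct for detecting an 11.5-point rise.

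If non-significance is taken as success, a true 5-point rise would pass 58% to 84% of the time, and the design rise itself 10% to 21%. These figures rest on one pair per subject, reverse discordance of 0.005 and the assumed meaning of cell 1,2. Pooling the two sites as independent pairs lowers the 5-point figure to 24% to 38%. That the plan will read its result this way is an inference; that no criterion is stated is not. The rule has to be set before the data are seen.

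**What to change.** For each spray, make the primary analysis the two-sided 95% confidence interval (Tango score, for example) for the paired difference in the proportion of swabs with growth, post-spray minus post-chloraprep. Conclude that sterility is maintained only if the upper limit lies below a pre-stated, justified margin no larger than 0.115. Report the interval whatever the result. State that a non-significant McNemar test alone does not support the hypothesis, how the wrist and back pairs are combined, and what role the colony counts have.

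The 0.115 is a ceiling taken from the plan's own detectable difference and is not a recommended margin, since a true 5-point rise would still pass 31% of the time there.

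Restate the power under this rule. With 72 pairs the chance of success at 0.115 is good if discordance is low (88% or more up to 3% each way), but 71% at the plan's 12.5% in total. For information, an 80% chance needs about 91 pairs at margin 0.115 and 12.5% discordance. At margin 0.05 it needs about 124, 177, 232 or 413 pairs for 1%, 2%, 3% or 6.25% each way.

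The cost is protocol wording, a justified margin, one interval per spray and a restated power statement. Data collection need not change. The conclusion becomes that a rise above the margin is ruled out, in place of no effect, and a tight margin may be out of reach with the planned sample.

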### 2) SUBJECT POPULATION AND ELIGIBILITY

We plan to ask for volunteers from Henry Ford employees. Our exclusion criteria will include people who have infections at the site or have a history of hypersensitivity to either the numbing sprays or chloraprep.

#### 3) STUDY PROCEDURES

Our study will involve swabbing and culturing the skin of volunteers on the wrist where an arterial line is place, as well as on the lower back where an epidural is placed. First, a swab of the untreated area of wrist or lower back will be performed. Second, the section of skin will be treated with chloraprep according to standard procedure prior arterial line or epidural placement, and this treated skin will be swabbed. Third, the chloraprep-treated section of skin will be treated with numbing spray (either Gebaur's Ethyl Chloride or Pain Ease). For the Pain Ease group, the spray will be applied up to 10 seconds or until white appears (whichever comes first). If frosting appears, stop. The area that has been subsequently treated with chloraprep and numbing spray will then be swabbed. These swabs will be cultured by the HFHS microbiology lab on agar plates for 48 hours and the number of colony forming units (CFU) will be counted. The amount of bacterial growth will be compared between the untreated samples, chloraprep samples and the associated post-spray samples. Funding for the project will be from Gebauer, the manufacturer of the numbing sprays. Based on power analysis, for each spray, a sample size of 72 subjects with 6 swabs taken per subject (subsequent untreated, chloraprep, and numbing spray samples taken from the wrist and lower back from each subject) achieves 80 % power to detect an odds ratio of 24 using a two-sided McNemar test with a significance level of 0.05. The odds ratio is equivalent to a difference between two paired proportions of 0.115 which occurs when the proportion in cell 1,2 is 0.12 and the proportion in cell 2,1 is 0.005. The proportion of discordant pairs is 0.125. As there are two separate sprays being investigated independently, the final number of subjects will be 144, with 6 swabs taken per subject.

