#### 4) ANTICIPATED RISKS

There are no likely risks to participants in this study. Less likely risks include hypersensitivity to the products, risk of frostbite, risk of skin pigment alteration, and Ethyl Chloride is a flammable substance. We will decrease the risk of frostbite by limiting exposure to the numbing sprays to the initial formation of crystals on the skin.

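### Do Sections 3 and 4 set conflicting limits on spraying, and is ethyl chloride left without one?

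*Combined protocol and SAP*

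**What the plan says.** Section 3 (Study Procedures) introduces the third step for both products together: "the chloraprep-treated section of skin will be treated with numbing spray (either Gebaur's Ethyl Chloride or Pain Ease"). The next sentence concerns one product only: "For the Pain Ease group, the spray will be applied up to 10 seconds or until white appears (whichever comes first"). A separate short sentence follows and names no product: "If frosting appears, stop". Nothing else in Section 3 says how long to spray or when to stop, and no sentence there gives a limit that names ethyl chloride.

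Section 4 (Anticipated Risks) lists frostbite and skin pigment change among the less likely risks and commits the investigators to a limit: "We will decrease the risk of frostbite by limiting exposure to the numbing sprays to the initial formation of crystals on the skin". The plural takes in both products.

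The protocol does not define *white*, *frosting* or *crystals*, and does not say whether they are one visible sign or several. The section on data analysis mentions a spreadsheet but does not list spray duration as an item to record.

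**The concern.** Three features make this look like a fault.

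- **Different triggers.** Section 3 works with a time ceiling, whitening and frosting. Section 4 works with first crystals. A reader could conclude that following one section does not deliver what the other promises.
- **One product named.** The only limit in the procedure tied to a named spray is for Pain Ease. If the frosting sentence belongs to the Pain Ease rule, the procedure itself says nothing about when to stop ethyl chloride.
- **Exposure is the intervention.** The study asks whether spraying prepped skin contaminates it, and Section 1 makes further studies depend on the answer. If operators applied ethyl chloride for widely differing times, a finding of no increase in growth would be harder to tie to a known application.

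There is a safety side as well. Participants are volunteers with no expected benefit (Section 5). Section 12 on monitoring speaks only of data quality. The exposure limit is therefore the only frostbite precaution the protocol describes.

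**Working it through.** **1. Does any figure in the plan depend on the exposure rule?** The sample size is the only design calculation, so I reproduced it first. All inputs are from Section 3: "the proportion in cell 1,2 is 0.12 and the proportion in cell 2,1 is 0.005"; two-sided McNemar test, level 0.05, power 80%.

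- Difference: d = 0.12 − 0.005 = 0.115
- Discordant proportion: p = 0.12 + 0.005 = 0.125
- Odds ratio: 0.12 / 0.005 = 24
- n = [z(0.975)·√p + z(0.80)·√(p − d²)]² / d²
- n = [1.960 × √0.125 + 0.842 × √(0.125 − 0.013225)]² / 0.013225 = 71.78, rounded up to 72

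This matches the plan's 72 per spray. Spray duration is not an input, so the figure neither supports nor weakens the concern.

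**2. How many applications are involved?** Each spray has 72 volunteers, each with a wrist and a lower-back site: 72 × 2 = 144 sprayed sites per spray. This is a count of sites to which the wording applies. It does not estimate added risk or bias.

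**3. Is there a stop point for each spray?** The frosting sentence can be read in two ways.

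| Reading of the frosting sentence | Pain Ease | Ethyl chloride |
|---|---|---|
| Pain Ease only | Section 3: 10-second ceiling, whitening, frosting; Section 4: first crystals | Section 4: first crystals |
| Both sprays | Same as above | Section 3: frosting; Section 4: first crystals |

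No cell is empty. On either reading ethyl chloride has a written limit, although on the first reading it sits in the risk section and not in the procedure.

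**4. Can both sections be followed at once?** For Pain Ease, Section 3 sets an upper bound on time and ends sooner if whitening appears. Ending at or before 10 seconds, with no crystals seen, satisfies Section 4. If frosting and crystals are the same sign, the two stops coincide. A conflict would arise only if the Section 3 sign came after first crystals and an operator kept spraying in between. The documents give no such ordering. For ethyl chloride, Section 3 contains nothing that runs against Section 4.

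**5. Would varying exposure distort the comparison?** Section 3 compares each post-spray sample with the associated chloraprep and untreated samples from the same person, and states that the two sprays are investigated independently. A difference in exposure between sprays therefore enters no planned contrast. Within a spray, the plan defines application by a visible sign, so some variation in seconds between volunteers is part of the intervention as written. Even the Pain Ease rule fixes only a maximum.

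**The case for a change.** The best case for a change is that a limit belongs where staff look for it. The frosting sentence comes directly after one confined to Pain Ease and could fairly be read as part of it. Even if it covers both products, ethyl chloride has no time ceiling in either section. Whitening and frosting are given in separate sentences: if they are one event, the second sentence is redundant for Pain Ease; if they are two, at most one can be the same as first crystals, and the reader is not told which. Without recorded durations, nobody could check afterwards how exposure varied, and brief applications could look reassuring without representing later use.

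Part of this stands. The terms are undefined and differ between sections, and Section 3 has no limit naming ethyl chloride. The rest does not carry through. Lacking a time ceiling is different from lacking a stop point, and Section 4 supplies one as a commitment by the investigators. In a protocol this short, nothing suggests that staff would work from Section 3 and ignore Section 4. The effect on the result is asserted only: the documents give no relation between seconds of spraying and colony counts. A duration column would add description, but no planned comparison would use it.

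**Conclusion.** The concern does not hold as a fault in the plan. Sections 3 and 4 use different, undefined words for the end of spraying, but they can be followed together, and every one of the 144 volunteers is covered by a written stop point. The sample size of 72 per spray is unaffected, and no planned comparison is shown to be biased.

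This rests on two assumptions: that the protocol is read as a whole, so that the Section 4 commitment governs conduct for both products; and that the signs named in Section 3 do not come later than first crystals. The documents neither state nor contradict the second. If the clinical team knew it to be false, the passages would conflict and would have to be reconciled by that team. No view is taken here on which stop rule is clinically right. On the text as it stands, this is a wording gap that investigators can be expected to fill sensibly.

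### The post-spray swab always follows the post-chloraprep swab on the same prepped section, with no concurrent unsprayed swab, so spray effect, swab order and time since prep cannot be separated

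*Combined protocol and SAP*

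**What the plan says.** Section 3 (Study Procedures) sets one sequence for every volunteer and both sites. The untreated skin is swabbed and chloraprep is applied, "and this treated skin will be swabbed. Third, the chloraprep-treated section of skin will be treated with numbing spray". Then: "The area that has been subsequently treated with chloraprep and numbing spray will then be swabbed".

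The six swabs per volunteer are three conditions at two sites: "subsequent untreated, chloraprep, and numbing spray samples taken from the wrist and lower back from each subject". None is a late swab of prepped, unsprayed skin. There is no sham spray and no unsprayed group; the only other group receives the other spray.

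The text does not say whether the two post-prep swabs cover the same spot within the section, and it gives no interval between them. Two statements bear on the length of the sequence. For Pain Ease, "the spray will be applied up to 10 seconds or until white appears", whichever comes first. Section 4 (Anticipated Risks) speaks, for both sprays, of "limiting exposure to the numbing sprays to the initial formation of crystals on the skin".

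The sample size uses a two-sided McNemar test at 0.05 with 72 volunteers per spray, where "the proportion in cell 1,2 is 0.12 and the proportion in cell 2,1 is 0.005". The section on data analysis describes no handling of order or time.

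**The concern.** The aim in section 1 is causal: does the spray contaminate prepped skin? The paired comparison instead estimates the spray effect plus the effect of having swabbed once already plus the effect of extra time since the antiseptic. These three change together in every pair, so no analysis can separate them and more volunteers would not help.

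The errors can run in opposite directions. If the second swab covers a spot already swabbed, it meets fewer residual organisms; longer antiseptic action would work the same way. Both favour the study's own hypothesis that "there will not be a significant increase in bacterial growth after ethyl chloride or pain ease spray". Organisms picked up from the surroundings in the interval would instead be attributed to the spray.

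The result carries weight: "Depending on the results of this study we will decide if it is safe to proceed to additional studies".

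**Working it through.** **Inputs from section 3.** p12 = 0.12, p21 = 0.005, so discordance pd = 0.125 and difference d = 0.115; 72 pairs per spray; two-sided α = 0.05; power 80%.

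**1. The plan's own figure.** n = [z(0.975)·√pd + z(0.80)·√(pd − d²)]² / d² = [1.960 × 0.3536 + 0.8416 × 0.3343]² / 0.013225 = 0.9743² / 0.013225 = 71.8, rounded up to 72. Power at 72 is 0.801 by this approximation and 0.789 by exact McNemar. The sample size reproduces; the problem is bias, not precision.

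**2. What each swab carries.**

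| Swab | Chloraprep | Spray | Order | Time since prep |
|---|---|---|---|---|
| Untreated | no | no | 1 | – |
| Post-prep | yes | no | 2 | earlier |
| Post-spray | yes | yes | 3 | later |

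Between the second and third rows, spray, order and time all change at once, for every volunteer and site.

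**3. Masking by the earlier swab.** Assume the two swabs overlap fully, organism counts are Poisson and the first swab removes a share r. If P is the chance of post-prep growth on an untouched spot, the second swab grows with probability 1 − (1 − P)^(1 − r), so masking = P − [1 − (1 − P)^(1 − r)]. The documents give neither P nor r. With r = 0.5:

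- P = 1%: 0.0100 − (1 − √0.99) = 0.0100 − 0.0050 = 0.5 points
- P = 5%: 0.0500 − (1 − √0.95) = 0.0500 − 0.0253 = 2.5 points
- P = 10%: 0.1000 − (1 − √0.90) = 0.1000 − 0.0513 = 4.9 points

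At P = 5%, r = 0.3 gives 0.0500 − (1 − 0.95^0.7) = 1.5 points and r = 0.7 gives 0.0500 − (1 − 0.95^0.3) = 3.5 points. If the spots do not overlap, masking is zero. This applies only to flora left after prep; organisms that the spray brings arrive after the earlier swab and cannot be removed by it.

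**4. Pick-up in the interval.** Assume the spray does nothing and set p12 to a pick-up rate e, keeping p21 = 0.005. The net shift is then e − 0.005. The chance of a significant increase, per exact two-sided McNemar test on 72 pairs, is:

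- e = 1%: 0.0001
- e = 2%: 0.0023
- e = 5%: 0.1135

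These are per test. The plan has two sprays and two sites and does not say whether sites are pooled, so they are not rates per study.

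**5. Price of a concurrent control patch.** Two patches may differ by chance. Adding discordance δ to each cell (p12 = 0.12 + δ, p21 = 0.005 + δ) at 72 pairs gives:

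| δ | Normal approximation | Exact | Pairs for 80% (exact) |
|---|---|---|---|
| 0 | 0.801 | 0.789 | 74 |
| 0.005 | 0.768 | 0.736 | 81 |
| 0.01 | 0.736 | 0.689 | 88 |
| 0.02 | 0.678 | 0.610 | 101 |

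Spray reaching the control patch also shrinks the contrast. If 10% of spray-caused growth appears there, the difference is 0.12 × 0.90 − 0.005 = 0.103, or 10.3 points. Combined with δ = 0.01 (p12 = 0.118, p21 = 0.015), exact power is 0.60.

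**The case against.** The best defence is that the effect is probably small and the cure may cost more than the disease. The spraying limits suggest a short sequence. Pick-up of 1% or 2% almost never yields a false increase, and nothing in the documents supports 5%. Same-site pairing avoids between-patch variation and follows the order of intended use. A split field loses power and risks drift, and both make a finding of no increase easier to obtain. Space at the wrist may also be tight.

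Much of this stands. It rules out calling the confound cheap to remove by a split field, and it supports putting the simpler change first. It does not remove the confound: a limit on spraying time does not fix the whole interval between swabs, and the documents contain nothing that shows the effect to be small.

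A reader might take cell 2,1 = 0.005 as a ceiling of 0.5 points on masking. It is not one. The cells are unlabelled, and 0.005 is a planning assumption from a scenario in which the spray does have an effect.

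In the other direction, a reader might infer that the design is biased toward no increase, or that it hides contamination brought by the spray. The documents do not support either: pick-up works against the first, and the earlier swab cannot remove what the spray later brings. Nor do they establish that the same spot is swabbed twice, only the same section.

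**Conclusion.** The point holds as a matter for consideration. Spray status is completely tied to swab order and time since prep, so the planned comparison cannot attribute a difference, or the lack of one, to the spray alone. Size and net direction are unknown.

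Under the stated assumptions, masking runs from zero (no overlap) to about 4.9 of the planned 11.5 points (full overlap, half of organisms removed, 10% post-prep growth). Pick-up matters for false positives only towards the top of the assumed 1% to 5% range. Longer antiseptic action cannot be sized from the documents. The sample-size calculation itself is not in error.

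**What to change.** **At minimum.** Mark non-overlapping spots beforehand for the untreated, post-prep and post-spray swabs. Keep the last two within the same prepped section, and fix and record the interval between them. This removes masking by the earlier swab at little cost: some protocol text, skin marking and a recorded time. It leaves time since prep tied to the spray, and the report should say so.

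**Better, where space allows.** Mark two patches within the prepped field at each site and randomise them to chloraprep only or chloraprep plus spray. Swab both at the same elapsed time after prep. Take the untreated swab before prep, outside both patches. Six swabs per volunteer and the McNemar test can stay.

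The cost is a randomisation list, enough prepped skin, spacing that keeps spray off the control patch, and a looser link between the untreated and chloraprep swabs. The prepped field should remain consistent with the standard procedure that section 3 cites.

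Power must be restated. At 72 pairs, added discordance of 0.5, 1 or 2 points each way gives exact power of about 74%, 69% or 61%, and 60% if 1 point is combined with 10% drift. Without drift, restoring 80% takes 81, 88 or 101 volunteers per spray, which over two sprays is 2 × 9 = 18, 2 × 16 = 32 or 2 × 29 = 58 more than the planned 144.

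### Section 3 specifies no neutraliser for antiseptic carried on swabs from chloraprep-treated skin, so a no-growth plate may not mean clean skin

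*Combined protocol and SAP*

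**What the plan says.** Section 3 (Study Procedures) sets three swabs at each of two sites. The first is from untreated skin. Chloraprep is then applied, "and this treated skin will be swabbed". Spray follows, and for the third swab: "The area that has been subsequently treated with chloraprep and numbing spray will then be swabbed".

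The laboratory method is one sentence: "These swabs will be cultured by the HFHS microbiology lab on agar plates for 48 hours", after which colonies are counted. The swab type, transport fluid, agar and plating method are not given. No section mentions a neutraliser or a check that bacteria on a swab from prepped skin can still grow. The Data Analysis section covers only how data are recorded.

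Section 1 states the hypothesis in these terms: "there will not be a significant increase in bacterial growth after ethyl chloride or pain ease spray have been added to skin treated with chloraprep". It also says what hangs on the answer: "Depending on the results of this study we will decide if it is safe to proceed to additional studies".

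The sample size in section 3 is, "for each spray, a sample size of 72 subjects with 6 swabs taken per subject", for 80% power with a two-sided McNemar test at 0.05.

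**The concern.** The contrast that answers the study question is the chloraprep swab against the post-spray swab. Both are taken after antiseptic has been put on the skin, so each may lift antiseptic along with any organisms. If that antiseptic stays active on the plate, organisms that were collected may not grow. A zero count then has two explanations, and nothing written in the plan separates them. The untreated swab cannot, because it is taken before any chloraprep is applied.

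The direction matters. The plan tests for a difference and gives no non-inferiority margin, so a non-significant result will be read as support for the hypothesis. A loss of assay sensitivity makes that result more likely whatever the spray does. The result then feeds a safety decision about further studies of the sprays as an alternative to lidocaine for invasive procedures such as arterial lines and epidurals. The loss could not be repaired at analysis, because a plate that failed to grow holds no information on why.

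**Working it through.** **Inputs from section 3.** n = 72 subjects per spray; two-sided alpha 0.05; power 80%; cell 1,2 = 0.12; cell 2,1 = 0.005.

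**Step 1: the plan's own figure.** Discordant proportion pd = 0.12 + 0.005 = 0.125. Difference d = 0.12 − 0.005 = 0.115. Odds ratio = 0.12/0.005 = 24. All three agree with the plan.

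n = [1.960·√pd + 0.842·√(pd − d²)]² / d²
= [1.960 × 0.3536 + 0.842 × 0.3343]² / 0.013225 = 71.8, rounded up to 72.

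Power at 72 = Φ[(d√n − 1.960·√pd) / √(pd − d²)] = Φ[(0.9758 − 0.6930)/0.3343] = 0.801. The exact two-sided binomial McNemar test, averaged over the number of discordant pairs, gives 0.789. The stated sample size reproduces.

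**Step 2: an illustration of suppression.** The documents give no figure for carry-over, so the suppressed share s is an assumption and is shown over a range. Further assumptions:
- s is the same on both post-chloraprep swabs.
- No pair is positive on both swabs.
- Cell 1,2 is the cell for growth after spray only. The plan does not label its cells.

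The cells then become 0.12(1 − s) and 0.005(1 − s). The odds ratio stays at 24, but the difference shrinks to 0.115(1 − s).

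| s | cell 1,2 | cell 2,1 | difference | power, plan's formula | power, exact |
|---|---|---|---|---|---|
| 0 | 0.12 | 0.005 | 0.115 | 0.80 | 0.79 |
| 25% | 0.09 | 0.00375 | 0.08625 | 0.67 | 0.56 |
| 50% | 0.06 | 0.0025 | 0.0575 | 0.50 | 0.23 |
| 75% | 0.03 | 0.00125 | 0.02875 | 0.28 | 0.02 |

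Example at 25%: pd = 0.09375, so Φ[(0.08625 × 8.485 − 1.960 × 0.3062)/0.2938] = Φ(0.448) = 0.67.

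**Step 3: why the exact figures fall faster.** An exact two-sided test needs at least six discordant pairs, all in one direction: 2 × 0.5⁶ = 0.031, whereas 2 × 0.5⁵ = 0.0625. The expected number of discordant pairs is 72 × 0.125 = 9 with no suppression, 72 × 0.0625 = 4.5 at 50% and 72 × 0.03125 = 2.25 at 75%.

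**Step 4: sensitivity to the second assumption.** If 5% of pairs were positive on both swabs (also an assumption) and the two plates were suppressed independently, each discordant cell gains 0.05·s(1 − s). Exact power becomes 0.48, 0.21 and 0.03 at 25%, 50% and 75%. The pattern is unchanged.

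**The case against.** The strongest reply is that the plan is silent, and silence is not absence. A reader might infer that swabs go onto plain agar with no neutralising step. Section 3 does not say that. It hands the culture to a hospital microbiology laboratory and gives only the plate and the duration, and a medium containing a neutraliser is also an agar plate. The laboratory may use one routinely. This stands, and it is why the point is put conditionally.

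A second reply is that the sequence of antiseptic, swab and agar does not prove that inhibition occurs. The documents do not describe how long chloraprep stays active, and they give no interval between its application and either swab. This also stands: both the occurrence and the extent of suppression are undocumented. What follows from the plan alone is that a negative plate is open to two readings.

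A third concerns the arithmetic. A reader might shrink only cell 1,2 and hold cell 2,1 at 0.005. That gives lower power: 0.65 (exact 0.53), 0.45 (0.20) and 0.20 (0.015) at the same three shares. It does not fit the mechanism, since both compared swabs come from chloraprep-treated skin, so those figures overstate the loss.

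None of this removes the point. Culture is the study's only outcome measure, and a written plan should let its reader interpret a negative plate.

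**Conclusion.** The concern holds in conditional form. Section 3 specifies no neutraliser for swabs from chloraprep-treated skin. Unless the laboratory already uses one, a no-growth plate after spray cannot be attributed to clean skin alone, and comparable suppression on both compared swabs would favour the study's hypothesis.

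The size is unknown. The fall in exact power from 0.79 to 0.56, 0.23 and 0.02 is a set of scenarios resting on the assumptions listed in the working, not an estimate for this study. With no suppression, power stays at about 80%.

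Two stronger conclusions are not supported. The documents do not show that the assay cannot see contamination. Nor do they show that the sample size is wrong: it is correct on its own inputs, which take each plate to show the true state of the skin.

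**What to change.** In section 3, require all six swabs per volunteer, including the untreated swab so that handling is the same throughout, to be collected in or plated on a medium with an antiseptic neutraliser chosen by the microbiology laboratory. Have the laboratory confirm, before the first volunteer is swabbed, that the medium neutralises chloraprep; without that check the two readings of a negative plate would still not be separated. If the laboratory already works this way, naming the medium and the check in section 3 is enough.

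The cost is a sentence or two of protocol text, a modest supply cost over 144 × 6 = 864 swabs and a small bench check. The documents give no prices. No extra volunteers or volunteer swabs are needed.
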